### **(iii) Secondary Endpoint Analysis**

Secondary outcomes will be analysed using the appropriate generalised linear model depending on the distribution of the outcome, like linear regression for continuous and logistic regression for binary outcomes. When measurements are collected at multiple time points, repeated measurements mixed models will be used. All implant pacing parameters will be recorded including X-ray time as a surrogate for procedure time and pacing thresholds, sensed R wave, impedance and pacing amplitudes. These metrics will be compared between arms.

Quality of life will be assessed over time and treatment groups compared using longitudinal analysis with appropriate recognition for informative dropout, using joint modelling to account for events.

Our planned subgroup analyses will be performed by adding the interaction term between treatment and the subgroup variable into the model.

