### *1) His bundle pacing:*

The pacing stimulus captures the specialised His-Purkinje conduction system, producing normal, rapid and coordinated biventricular activation and contraction. Many centres have avidly taken up conduction system pacing, producing an increasing body of observational data, which now has systematic reviews and meta-analyses. These data show that His bundle pacing can be safely delivered and will chronically in the main remain stable. Pacing thresholds are typically slightly higher than RV pacing (mean 1.3V versus 0.59V) and procedural times slightly longer (70 minutes versus 55 minutes), as seen in a recent 765-patient observational study. There is a ~7% lead reintervention rate which is similar to that reported for LV leads. However, these potential disadvantages appear to be offset by more physiological ventricular activation as evidenced by narrower paced QRS complexes (128ms versus 166ms with RV pacing) and subsequent improved cardiac function. In the mentioned observational study these physiological improvements, in patients who required more than 20% ventricular pacing, were associated with a lower rate of death and heart failure hospitalisations when compared with RV pacing (25.3% vs 35.6%, p = 0.02). Although promising, these findings need to be tested in an adequately powered randomised control trial.

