## 1.2 Need for RCT

Physiological pacing strategies may be associated with slightly longer procedural time, higher thresholds and slightly higher lead related complications than RV pacing which has been the standard of care of >60 years. However, whether these potential issues are offset by the potential benefit of improved cardiac activation and therefore function needs to be determined in an adequately powered RCT. This is what PROTECT-HF aims to do.

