#### Procedural Steps (recommendations)

- 1) Consider identifying the His bundle location; find a His EGM OR **fluoroscopically** identify approximate location utilising contrast to identify the tricuspid valve ring
- 2) Position delivery catheter to a location **~2cm** more **distal** along the septum utilizing the **RAO** projection. *It is possible to do this without step 1.*
- 3) Check **septal orientation** in **LAO** projection. Often need **counter-clockwise** catheter torque to hold sheath on septum
- 4) Consider **pacing** to check undeployed **impedance** and initial pacing response - observe leads II and III, ideally divergent with **lead II positive**. Look for **proximal notch** in **V1** suggesting early activation of the RV
- 5) Perform **~10-15 rapid turns** (if using Medtronic 3830 lead) in **LAO**, watching for lead movement through the septum. Observe closely for **narrow RBBB ectopic beats** in **V1**. If see these stop screwing. (less turns with stylet driven lead)
- 6) Check **pacing response** – the R wave in **V1** should move toward end of QRS with evidence of acceptable LBBP. If not achieved consider **further lead rotations**. Caution performing further deployment if impedance **<450ohms**.

\* If struggling to **penetrate** the septum move to a different septal location

[figure not shown]

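### X-ray time is compared between arms as a stand-in for procedure time, although the protocol gives no reason to expect X-ray to take the same share of the procedure in both arms

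*Protocol*

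**What the plan says.** Protocol section 7.3 (iii), Secondary Endpoint Analysis, states that the implant parameters are to be recorded, "including X-ray time as a surrogate for procedure time". Thresholds, sensing, impedance and amplitudes are in the same list, and the text continues: "These metrics will be compared between arms".

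Procedure time also appears in the background. Section 1.1, under His bundle pacing, cites an observational study with "procedural times slightly longer (70 minutes versus 55 minutes" for RV pacing. Section 1.2 says: "Physiological pacing strategies may be associated with slightly longer procedural time, higher thresholds and slightly higher lead related complications". It then says that "whether these potential issues are offset by the potential benefit of improved cardiac activation and therefore function needs to be determined" in an adequately powered trial.

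No section of the protocol names direct recording of procedure duration. The Visit Schedule (4.4) and the Implant Visit list (4.6) show no start or end time. The eCRF and its manual (9.2, 9.3) are not part of the document.

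**The concern.** A surrogate compared between randomised arms has to relate to its target in the same way in both. Here the link is the fraction of the procedure spent under X-ray, and that fraction is itself a result of the allocated technique. Randomisation stratified by site does not balance it, because it is not a baseline characteristic. A larger sample does not reduce the distortion, because it is systematic.

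At stake is the description of one of the costs that section 1.2 sets against the hoped-for benefit. If the X-ray contrast is reported as a contrast in procedure time, its size and possibly its sign could be wrong, and nothing in the data would show it unless duration were also recorded. The choice of measure is made in the protocol, and a later analysis plan cannot repair it if clock times were never collected.

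**Working it through.** **Step 1: what differs between the arms.** The protocol describes work specific to the physiological arm, of two kinds.

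- *Guided by X-ray.* The left bundle steps in section 3 (Procedural Steps) position the catheter and check septal orientation in named fluoroscopic projections, and the operator watches the lead advance through the septum. If conduction system pacing fails or its parameters are not acceptable, section 4.5 calls for a coronary sinus lead.
- *No stated need for X-ray.* Finding the His bundle is optional and can be done by electrogram or by fluoroscopy with contrast ("Consider identifying the His bundle location; find a His EGM OR" introduces the choice). Pacing responses and impedance are checked. Capture is assessed by changing the output (section 3, His Capture and Hallmarks of acceptable LBB Capture). Section 4.5 adds testing for infra-Hisian block at higher paced rates and requires a recorded capture-transition manoeuvre.

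The first kind tends to raise the X-ray share and the second to lower it. The protocol gives no duration or X-ray time for any step in either arm, so the net effect is unknown.

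**Step 2: inputs.**

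- Procedure time: 70 minutes (His bundle pacing) and 55 minutes (RV pacing), from section 1.1. Difference 70 − 55 = 15 minutes; ratio 70/55 = 1.27.
- X-ray share of the procedure: not in the document. Let f be the share in the RV arm and k the ratio of shares, physiological over RV. Assumed range for k: 0.6 to 1.5.

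The plan states no figure for X-ray time, so there is none to reproduce.

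**Step 3: formula.** X-ray time = procedure time × share. Then

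X-ray ratio = (70 × f × k) / (55 × f) = (70/55) × k = 1.27 × k.

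The RV share f cancels, so the surrogate multiplies the true ratio by exactly k. The difference in X-ray minutes is f × (70k − 55), shown below for an assumed f of 0.2.

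| k (assumed) | X-ray ratio | X-ray difference at f = 0.2 | Reading |
|---|---|---|---|
| 0.6 | 0.76 | −2.6 min | direction reversed |
| 0.786 | 1.00 | 0.0 min | difference hidden |
| 1.0 | 1.27 | +3.0 min | ratio correct |
| 1.25 | 1.59 | +6.5 min | exaggerated |
| 1.5 | 1.91 | +10.0 min | exaggerated |

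**Step 4: break-even.** The X-ray ratio equals 1 when k = 55/70 = 0.786, that is, when the physiological share is about 21% lower than the RV share (1 − 0.786 = 0.214). Below that the sign reverses; between 0.786 and 1 the difference is understated; above 1 it is overstated.

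**The case against.** The strongest reply is that this concerns a descriptive metric that the protocol openly calls a surrogate. Procedure duration is not among the objectives (2.1 to 2.3), and neither it nor X-ray time is among the endpoints (2.4, 2.5). A reader might infer from section 1.2 that the trial cannot answer its own question about longer procedures. The text does not support that: the question set there is whether possible disadvantages are offset by benefit, and the primary endpoint of death and unplanned heart failure care is what mainly addresses it. This part of the reply stands in full.

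A second reply concerns direction. One might infer that most of the extra time in the physiological arm is spent without X-ray, so that the comparison will reverse. The document does not say so. Its left bundle steps rely substantially on fluoroscopic views, and a longer placement may well bring more X-ray time. Reversal needs a share more than about 21% lower, and nothing in the protocol indicates that. This also stands, and it is why the result is given as a range in both directions. It does not support an equal share, which is what the surrogate requires.

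Third, the list in 7.3 (iii) is introduced as inclusive rather than exhaustive, and the eCRF is not shown, so start and end times may already be collected. That is possible, and the fix is worded accordingly. The surrogate wording would then be unnecessary.

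Finally, clock time has its own asymmetry: the capture evidence required by section 4.5 is documentation work in the physiological arm only. This is a fair caveat when interpreting duration, but duration would still be measured directly rather than through an unknown multiplier.

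**Conclusion.** The point holds in limited form. The protocol fixes a between-arm comparison of procedure time through a measure that is valid only at k = 1, and its own technique descriptions leave equal X-ray shares unsupported. On the cited 70 versus 55 minutes, the apparent ratio could run from 0.76 to 1.91 over k from 0.6 to 1.5, against a true 1.27.

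This rests on two assumptions: that the cited observational times for His bundle pacing are a usable guide to this trial, which also allows left bundle and biventricular pacing, and that the range for k is plausible. The algebra needs neither, since whatever the true time ratio is, the surrogate multiplies it by k.

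The consequence is minor. The primary analysis, sample size, power, type I error and listed endpoints are untouched, and X-ray time remains a legitimate result as a measure of X-ray exposure.

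**What to change.** 1. If not already captured, add implant start and end times to the implant eCRF, with a stated definition of each applied alike in both arms. For participants already implanted, take them from catheter laboratory logs where available.
2. In section 7.3 (iii), compare procedure duration directly between arms, and report X-ray time separately as X-ray exposure.
3. Delete the phrase that makes X-ray time a surrogate for procedure time.
4. If times cannot be obtained, make the deletion anyway and draw no conclusion about duration.

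The cost is at most two data fields and one changed sentence, with no added procedure for participants. There are two downsides: some times will be missing for participants already implanted, and duration in the physiological arm will include the required capture documentation, which the report should say.

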### ***Planned Subgroup / Sub-study Analyses***

- i. *Mechanistic Echocardiographic Sub-study of 500 patients.* At trial enrolment, 500 patients will enter the Echo sub-study, with echocardiograms at baseline (within 6 weeks of implant) and 24 months later. The sub-study will analyse group mean effects and individual patient changes, focusing on LV volumes and ejection fraction. The data will be analysed using a core lab blinded to treatment allocation. We will also conduct an exploratory analysis using the AI technology developed and validated in our institution.

We have chosen LV end systolic volume as the primary endpoint variable of this sub-study because was found to be a powerful predictor of heart failure hospitalisations and mortality in previous clinical trials. A 10ml increase in volumes in the BLOCK HF study was associated with a 7% increase in death and 10% increase in heart failure hospitalisations.

The sample size is designed to detect a between-arm difference in change of LVESV of 10mls, with 90% power at the 5% significance level, assuming SD of differences is 27mls based on previous trials. We assume 7.5% cross over rate at implant but a dropout rate of 15% (because some patients may decline to attend for the follow-up echo when the time comes). This requires 426 patients. We plan to recruit 500 patients.

PROTECT HF	Protocol No: 22HH7931	Sponsor: Imperial College London	V9.0 16-Jun-2025
-------------------	--------------------------	-------------------------------------	------------------

- ii. *Effect of physiological pacing stratified by percentage of ventricular pacing.* Because randomisation is unlikely to affect the proportion of beats that require ventricular pacing, we will be able to validly analyse all the endpoints of the study with proportion of ventricular pacing as an input covariate. This means we may see a progressively larger difference between arms as the proportion of ventricular pacing increases. This will be a useful indicator for the mechanism of any effect seen.
- iii. *By pre-implant LV function.* Similarly, we will test whether pre-implant (clinically documented without cost to the BHF) ejection fraction predicts the difference in outcomes between arms.
- iv. *By pacing type.* On-treatment analysis is planned that will report outcomes for: selective His bundle pacing, non-selective His bundle pacing, selective left bundle pacing, non-selective left bundle pacing and pacing via the coronary sinus. Capture type will be adjudicated by blinded committee reviewing predefined manoeuvres designed to confirm the type of capture present. 12 lead ECG's and intracardiac electrograms will be collected at the time of implantation. 12 lead ECG's will also be collected during in person pacing follow up.
- v. *NHS Digital follow up.* For England-recruited patients we plan to utilise NHS digital data to confirm mortality status and hospital episodes for the duration of the study. We anticipate ~1500 patients will be recruited from England.
- vi. *Cost Effectiveness analysis.* Data as recommended by our health-economist for cost effectiveness analysis will be collected; health care utilization including number of hospital admissions, days in hospital, other unplanned visits to hospital, GP and outpatient visits.

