A CSP Capture adjudication committee will review all implant data at 6 monthly intervals to provide an assessment of whether CSP was achieved. If operators have high cross over rates or failure rates to deliver CSP they will be asked to undertake further training.

**Device Programming:** Programming is at the discretion of the clinical team. Pacing avoidance modes are advised, as per guidelines, with one modification. Unlike RV pacing, physiological pacing need not be avoided in patients with very long AV delays, (physiological pacing does not induce dramatic mechanical dyssynchrony which would otherwise be present with obligatory dual-chamber RV pacing) therefore DDD modes with shorter AV delays are acceptable or utilising programming options that mode switch with prolonged AV intervals. Ultimately programming decisions are at the discretion of the implanting physician as the trial aims to test the implantation strategy.

Initial data will be collected on patients pacing indication, comorbidity and medication. Pacing data will be collected from implant including paced ECG and threshold data to demonstrate the type of capture delivered. This will be adjudicated by a core lab based at Imperial College London to confirm capture type for subsequent analysis by pacing type.

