#### (ii) Exclusion criteria

- Patients who are likely to only need occasional ventricular pacing, i.e. those with isolated sick sinus syndrome.
- Pregnant women.
- Unable to provide informed consent.
- Those with comorbidity leading to a life expectancy <1year.

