#### 4.3 Randomisation and Blinding

Randomisation will take place using a fully validated, high quality, real-time electronic data capture system (OpenClinica database). Randomisation will be 1:1 between receiving ventricular myocardial pacing from a lead in the Right Ventricle versus a Physiological Pacing approach. Randomisation will occur once a patient has signed the informed consent form. The randomisation list will be programmed by the statistician using variable block length and stratified by site. Patients will be blinded to treatment allocation in a single blinded fashion. All endpoints will be adjudicated by blinded committee of clinicians with expertise in heart failure.

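### The pacing-percentage analysis is called valid because pacing need is unaffected by randomisation, but it uses delivered pacing, which section 3 lets differ by arm

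*Protocol*

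**What the plan says.** Item ii of Planned Subgroup / Sub-study Analyses, within section 7.3 (not 7.3(ii), which is the primary endpoint analysis), gives this justification: "Because randomisation is unlikely to affect the proportion of beats that require ventricular pacing, we will be able to validly analyse all the endpoints". It then names the variable: the endpoints are to be analysed "with proportion of ventricular pacing as an input covariate". It expects that the arms may separate further as pacing rises, and would read such a pattern as evidence on mechanism.

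The pacing variable is defined elsewhere. Sections 4.4 and 4.10 collect percentage pacing from the device during follow-up, and section 7.3(i) forms populations with mean pacing above 20%, 40% and 80% during the trial.

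On programming, section 3 says: "Pacing avoidance modes are advised, as per guidelines, with one modification". The modification is: "Unlike RV pacing, physiological pacing need not be avoided in patients with very long AV delays", and "therefore DDD modes with shorter AV delays are acceptable or utilising programming options that mode switch with prolonged AV intervals". The decision rests with the implanter: "Ultimately programming decisions are at the discretion of the implanting physician as the trial aims to test the implantation strategy". Section 4.3 blinds the patient: "Patients will be blinded to treatment allocation in a single blinded fashion".

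**The concern.** The argument starts from beats that *require* pacing and ends with pacing that was *delivered*. Randomisation cannot change need. It can change delivery wherever programming depends on the arm, and section 3 allows that in a subset. Delivered percentage is therefore a post-randomisation variable that allocation may influence.

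If some patients with residual AV conduction exceed a given pacing level in one arm only, the arms contain different mixes of patients at that level. If those patients also differ in prognosis, a gradient can appear with no treatment effect, or a real one can be blurred. The claim covers all endpoints, and the protocol has already said how it would interpret the gradient. Item iii of the same list treats pre-implant ejection fraction as a similar case, but that is a genuine baseline variable.

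**Working it through.** The protocol attaches no figure to this analysis, so there is none to reproduce. The check compares the passages and then illustrates the possible size.

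**The text**

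1. Premise: need for pacing is unaffected by allocation (item ii). This is reasonable.
2. Variable: device-recorded pacing after implant (sections 4.4, 4.10, 7.3(i)). Item ii does not tie the covariate to a pre-randomisation measure of need.
3. Programming: avoidance is advised in general but relaxed for physiological pacing in patients with very long AV delays (section 3).
4. Decision-maker: an implanter who knows the arm (sections 3 and 4.3).
5. Who is affected: first-degree block and Wenckebach are eligible (section 3.1(i)), so the subset is not empty. In permanent complete AV block or after AV node ablation, delivered pacing and need nearly coincide.

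Two patients with equal need can thus have different delivered percentages because of allocation.

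**Size at the 20% cut**

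From the documents: 2600 patients randomised 1:1, so 1300 per arm (sections 7.2, 4.3), and a 27.5% event rate (section 7.1), applied here to both arms.

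Assumed:
- s, the share with residual conduction: 0.1, 0.2 or 0.4
- f, the fraction of these above the cut in the physiological arm: 0.5 (RV arm: 0); call them movers
- r, the event-rate ratio of permanently paced to non-moving residual-conduction patients: 0.67 to 1.5
- m, the event-rate ratio of movers to non-movers: 1 at first
- h, the true effect in permanently paced patients: 1 at first (no effect)

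Formulas:
- Above-cut ratio = {[(1−s)·r·h + s·f·m] / [(1−s) + s·f]} / r
- Below-cut ratio = 1 / [(1−f) + f·m]
- SE of log ratio = √(1/d₁ + 1/d₂), with d = 0.275·n in each arm

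Example, s = 0.1 and r = 1.5: [(0.9×1.5 + 0.05) / 0.95] / 1.5 = 0.982. Patients above the cut: 1300×0.95 = 1235 v 1300×0.90 = 1170. SE = √(1/339.6 + 1/321.8) = 0.078. Bias = |ln 0.982| / 0.078 = 0.23 SE.

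| s | Above-cut ratio, r = 1.5 / 0.67 | n above cut | SE | Bias in SE |
|---|---|---|---|---|
| 0.1 | 0.982 / 1.026 | 1235 v 1170 | 0.078 | 0.23 / 0.33 |
| 0.2 | 0.963 / 1.055 | 1170 v 1040 | 0.081 | 0.46 / 0.66 |
| 0.4 | 0.917 / 1.123 | 1040 v 780 | 0.090 | 0.96 / 1.29 |

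With m = 1 the below-cut ratio is 1.00. The 40% row is extreme, because section 3.1 excludes "Patients who are likely to only need occasional ventricular pacing, i.e. those with isolated sick sinus syndrome".

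**If movers differ in risk (s = 0.1)**

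- m = 0.67: below-cut ratio 1/0.835 = 1.198; above-to-below contrast 0.811 (r = 1.5) or 0.835 (r = 0.67).
- m = 1.5: below-cut ratio 1/1.25 = 0.80; contrast 1.25 or 1.33.
- Only 65 v 130 patients lie below the cut, so the SE of the log ratio there is √(1/17.9 + 1/35.8) = 0.29.

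**If the effect is real (h = 0.78, none in residual conduction, m = 1)**

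The above-cut ratio is 0.774 / 0.818 at s = 0.1 and 0.767 / 0.859 at s = 0.2.

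**Continuous covariate**

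A Poisson model with arm, percentage and their product was fitted to expected values under no effect. Permanently paced patients and movers were set at 95%, the others spread over 1–39%. The false contrast between 95% and 20% pacing is 0.983 / 1.024 at s = 0.1 and 0.964 / 1.051 at s = 0.2. This is a different scenario from the cut-point model, since about half of the non-movers exceed 20%.

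**A separate illustration at the 80% cut**

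Assumed: a 10–30% share with long AV delay; of these, 10% paced above 80% in the RV arm and 50–80% in the physiological arm; 90% of other patients above 80% in both arms; hazard in the subset 0.5–1.0 times that of the others. With no treatment effect the ratio is 0.88–1.00 above the cut and 1.00–1.28 at or below it. Where the subset has the lower hazard, this false gradient runs in the direction item ii anticipates.

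**The case against.** Section 3 is permissive. It says what need not be avoided and what is acceptable, and it also allows mode-switching options. The exception concerns very long AV delays and has little bearing on slow atrial fibrillation, AV node ablation or permanent complete block. Patients likely to need only occasional pacing are excluded. The premise in item ii is hedged and is reasonable for most participants.

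The illustrated biases are small: at shares of 10–20% the above-cut ratio moves by less than 0.7 SE, even though half of the residual-conduction patients are assumed to cross the cut in one arm and none in the other. The largest contrast at a 10% share is under one SE (ln 1.33 = 0.285 against about 0.29). The bias is zero if the affected patients have the same prognosis as the rest. The delivered-percentage sets are already listed apart from the intention-to-treat analysis, and reporting detail may sit in a SAP.

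These points limit the likely size, and they stand. They do not rescue the validity claim: item ii makes it without qualification for all endpoints, section 3 of the same protocol undercuts it, and the mechanistic reading is fixed in advance.

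**Conclusion.** The concern holds and should be fixed. The statement that all endpoints can be validly analysed by proportion of ventricular pacing does not follow from its premise and conflicts with the Device Programming text. This conclusion rests on the protocol's wording and needs no numerical assumption.

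The size of any distortion cannot be derived from the documents, because the number of patients under the programming exception and their prognosis are not given. On the assumptions shown, bias in the above-20% set is modest at shares of 10–20%. The between-stratum contrast, which is what the mechanistic reading depends on, is more exposed if movers differ in risk: 0.81 to 1.33 at a 10% share, with poor precision. All of these biases vanish if the affected patients share the prognosis of the rest. The intention-to-treat primary analysis is not affected.

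**What to change.** 1. Delete the validity claim in item ii and reconcile the item with the Device Programming text in section 3. No view is taken here on how devices should be programmed.
2. Base the effect-modification analysis on pacing need known before randomisation, namely baseline pacing indication. Section 4.2 already reviews it at screening, section 7.3(i) already lists complete AV block at baseline, and section 7.3(iii) already plans the treatment-by-subgroup interaction. Split permanent from intermittent block only if the eCRF records it, since the inclusion criteria pool the two.
3. Keep the delivered-percentage analyses, including the 20%, 40% and 80% sets, labelled exploratory and non-randomised.
4. Report delivered pacing percentage by arm.

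The cost is a wording change and one descriptive table. No planned analysis is lost, and no new data are needed. The downside is that baseline indication predicts pacing burden less sharply than delivered percentage does.
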